The progressive accumulation of Gb-3 and its deacylated form lyso-Gb-3 creates an inflammatory environment (Figure 1). Furthermore, the accumulated Gb-3 and lyso-Gb-3 have been released into the cellular milieu from the ruptured lysosomes, leading to cell damage (2). Naturally sequestered inside live cells, these molecules are passively released extracellularly upon cell death and loss of membrane integrity. The elevated levels of both molecules in plasma and urine correlate with the impact of Fabry disease and may correspond to the short-term response to therapy with the reversal of cellular apoptosis.

Cells can die through several different mechanisms. Two of the significant types of cell death are necrosis and apoptosis. Sphingolipids are associated with apoptosis, where cells die while maintaining the integrity of their plasma membrane but are ingested by the tissue macrophages, in turn releasing pro- or anti-inflammatory signals such as TGF-beta or IL-10 (3). In contrast, necrotic cell death occurs in response to an insult such as infection and is associated with rapid loss of cell membrane integrity. Pyroptosis is a form of necrotic cell death due to a pro-inflammatory response (4). This pathway is uniquely dependent on Caspase-1, which is not involved in apoptotic cell death. Caspase-1 activation in macrophages results in the processing of Il-1 β with subsequent activation of the transcription factor NF- κ B.

The transcription factor NF- κ B regulates multiple aspects of immune functions and serves as a pivotal mediator of inflammatory responses (5). NF- κ B controls the expression of pro-

inflammatory cytokines (e.g., IL-1, IL-6, IL-8, and TNF α), chemokines (e.g., MIP-1, MCP1, RANTES, and Eotaxin), and vascular adhesion molecules (e.g., ICAM1, VCAM1, and E-selectin). NF- κ B is also a central mediator of TGF- β 1, the pathway central to the progression of fibrosis in multiple organs.

The responses induced by cell injury can cause significant damage while trying to heal the injured tissue. This is one of the reasons why it's important to elucidate these molecules in the urine not only to understand the order of pathogenic events associated with renal injury but also potentially block the cellular triggers of inflammation. Thus, this proposed study of pivotal urinary biomarkers may offer further insight on renal injury beyond current diagnostic tests.

[figure not shown]

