Common clinical biomarkers related to FD nephropathy (alpha-1-microglobulin, microalbumin, creatinine) will be compared with the pivotal biomarkers associated with the inflammatory and dysregulated immune pathways.

Table 2: Suggested pivotal biomarkers and pathways involved in Fabry nephropathy:

	Relationship to pathway or involvement	Biomarkers	
Inflammatory biomarkers	Cytokines	NF- κ B pathway	IL-1 β , IL-6, TNF- α , IL-10
		TGF- β 1 pathway	TGF- β 1, IL-4, INF-gamma
		TLR4 pathway	IL-18, IL-12
	Chemokines	NF- κ B pathway	MCP1, IL-8, RANTES, BAFF , APRIL
		TLR4 pathway	PAI-1
Biomarkers of kidney function and proteinuria	clinical laboratory urine biomarkers	alpha-1-microglobulin, albumin, cystatin C, GFR	
	We will measure in our laboratory	B2M, bikunin, NGAL, osteopontin, clusterin, creatinin.	
Acute kidney injury	Marker of renal tubular injury	KIM-1	
	Inflammation-associated glycoprotein	YKL-40	
	Growth factor, fibrosis	EGF	
	Apoptotic marker	CK-18 M30	
	Pyroptotic markers	IL-1β, IL-18 (included in the list of cytokines)	

This is a study to assess the markers related to autophagy, apoptosis, pyroptosis, and inflammatory markers related to NFkB, TNF-alpha, and TGF-β1 pathways in the urine. Urinary biomarkers will then be compared to the standard measures of kidney function and proteinuria: GFR, cystatin-C, B2M, bikunin, NGAL. Gb3 and Lyso-Gb3, urine microalbumin, and urine protein-to-creatinine (UPCR) ratio. We will also analyze the role of therapy, especially for the inflammatory responses in patients on stable enzyme replacement therapy (ERT) with that of patients naïve to therapy.

OBJECTIVE AND SPECIFIC AIMS

Primary objective: Identify biomarkers in urine for the detection and progression of kidney involvement in naïve male and female patients with FD, and compare with patients on ERT to assess the effects of ERT.

Specific Aims:

- 1) *To identify urinary inflammatory biomarkers associated with nephropathy in FD.*
- 2) *Analyze the association between urinary inflammatory markers, clinical urine biomarkers, circulating lyso-Gb3, and kidney involvement in naïve FD patients.*
- 3) *Analyze the association between urinary inflammatory markers, clinical urine biomarkers, circulating lyso-Gb3, and kidney involvement in FD patients on stable ERT.*

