- 4) *Assess the role of the time of initiation and duration of therapy (ERT), respectively, inactivation and reversibility of inflammation cascade, and how these relate to the degree of kidney involvement in patients with FD.*

SUBJECT SELECTION

Number of Subjects

A total of 50 subjects, male or female, between the ages of 18 to 80 years of age, include 25 healthy individuals and 25 patients with Fabry disease.

Study population

FD patients n=25 (5 without clinical evidence of nephropathy and 15 patients with clinical evidence of nephropathy), NAÏVE FD patients (n=5), and healthy controls n=25 (controls, urine samples are not actual patients, urine samples will be purchased from a commercial company).

The study will involve 50 age-and gender-matched subjects and controls divided into the following cohorts:

1. FD subjects without clinical evidence of nephropathy (normal eGFR and no microalbuminuria) naïve or on ERT (**n=5**),
2. FD subjects with clinical evidence of nephropathy (**n=15**)
 Subcohorts:
 - a. FD subjects on ERT with CKD stage 1 (estimation n=5)
 - b. FD subjects on ERT with CKD stage 2 (estimation n=5)
 - c. FD subjects on ERT with CKD type 3 a or b (estimation n=5)
3. FD patients naïve to therapy (**n=5**). Can we be included in Cohort group 1 or 2.
 Additional analysis will be stratified NAÏVE vs. ERT.
4. Non-FD age-matched controls with no known kidney disease n=25.

	FD	Healthy control
Total FD	25	25
without nephropathy	5	
with nephropathy	15	
NAÏVE	5	

Table 3. Clinical staging of FD patients:

Clinical parameter(s)	FD patients and kidney involvement				Age-matched controls
	Stage 1	Stage 2	Stage 3a	Stage 3b	
Kidney involvement					
Kidney damage	Normal/	Mild reduction	Moderate reduction	Moderate reduction	normal
GFR ml/m1.73 m ²	>90	60-89	45-59	30-44	90 min
Cystatin-C	0.5-0.9	1.0-1.2	1.3-1.5	1.4-1.9	0.5-0.9
Urine B2M	-	0.428-0.603	0.603-0.950	0.950-1.034	-
FD biochemical markers					
α-Gal A	Deficiency	Deficiency	Deficiency	Deficiency	Normal
GLA mutations	Yes	yes	yes	yes	No
Gb-3	Yes	yes	yes	yes	No
Lyso-Gb-3	Yes	yes	yes	yes	No

Gender of Subjects

Subjects of both genders will be included in the research, and it is expected that this inclusion will be representative of the FD patients population.

Age of Subjects

Subjects will be between the age of 18 to 80 years of age.

Racial and Ethnic origin

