There are no enrollment restrictions based on race or ethnic origin, and it is expected that racial and ethnic representations in this study will represent the FD population.

INCLUSION/EXCLUSION CRITERIA

Inclusion criteria:

- a. Male and Female subject is greater than 18 but not older than 80 years.
- b. Subject willing to sign the informed consent and/or assent.
- c. Confirmed diagnosis of Fabry disease based on deficient α -Gal A enzymatic activity and molecular analysis demonstrating pathogenic variants in the *GLA* gene.

Exclusion criteria:

- a. Any other known genetic condition associated with CKD,
- b. Evidence of hepatitis B or C infections or other chronic infectious diseases,
- c. Pregnancy or breastfeeding.
- d. Any other chronic condition, as per PI's discretion, that makes the subject ineligible.

Description of criteria for withdrawal from the study

A subject may withdraw from the study at any time. The study is entirely voluntary.

RECRUITMENT:

Upon identifying patients with FD disease by the Principal Investigator, the research coordinator will recruit the study subjects. The research coordinator will recruit healthy controls in the clinic or purchase from a commercial company.

SETTING/LOCATION

Research subjects will be recruited at the **Lysosomal and Rare Disorders Research and Treatment Center, Inc (LDRTC)** located at [name], and/or [name].

Subjects recruited at these facilities will be receiving advice from [name], and be under her clinical care. All experimental/laboratory procedures will be performed by or under the supervision of [name]. All informed consent processes will take place at the indicated research sites.

Laboratory tests will be performed at **Lysosomal & Rare Disorders Research & Treatment Center, Inc**, whereas some assays such as Lyso-Gb3 will be performed outside collaborating laboratories such as Labcorp Diagnostic Laboratories and/or Centogene, Rostock, Germany.

STUDY PROCEDURES

Study type

Descriptive and observational study of molecular components detected in biological specimens of urine.

Study design and plan

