This prospective study aims to establish novel biomarkers for non-invasive detection of kidney involvement in FD. FD patients will be assessed using the definition of Kidney Disease Outcomes Quality Initiative (KDOQI) 2002. The patients with CKD stages 3 or less with a progressive decline in kidney function, as evidenced by a decreasing GFR and a slope of less than -1.5, will be further assessed.

The glomerular filtration rate will be calculated from serum creatinine (CKD-EPI). The UPCR will be used to measure proteinuria. Additionally, the patients will be stratified as having low renal involvement (LRI) if the UPCR is less than or equal to 0.5 g/g. Anti-drug antibody status and other adverse events, such as the occurrence and the progression of cardiomyopathy as evidenced by LVMI, LVPWD, and neurological events such as strokes, will be recorded through the study. The categorization of kidney involvement via renal biomarkers will be defined (Table 4).

Table 4. Clinical staging of FD patients:

Clinical parameter(s)	FD patients and kidney involvement				Age-matched controls
	Stage 1	Stage 2	Stage 3a	Stage 3b	
Kidney involvement					
Kidney damage	Normal/	Mild reduction	Moderate reduction	Moderate reduction	Normal
GFR ml/min/1.73 m ²	>90	60-89	45-59	30-44	90 min
Cystatin-C	0.5-0.9	1.0-1.2	1.3-1.5	1.4-1.9	0.5-0.9
Urine B2M	-	0.428-0.603	0.603-0.950	0.950-1.034	-
FD biochemical markers					
α-Gal A	Deficiency	Deficiency	Deficiency	Deficiency	Normal
GLA mutations	Yes	yes	yes	yes	No
Gb-3	Yes	yes	yes	yes	No
Lyso-Gb-3	Yes	yes	yes	yes	No

The study will take place over 24 months. The clinical part of the active study to collect clinical data and the samples will be over 12 months. The urine samples will be collected three times (0, 6, and 12 months) (Table 5). A physical examination will be performed during the visits, and samples will be collected. We will review medical records as a part of the clinical evaluation. After a urine specimen collection, samples will be aliquoted and stored at -80⁰ C until biomarkers are screened. We expect to recruit the subjects within 6 months of the study initiation; thus, the last visit for the last subject is expected to be 19 months after the study starts.

Table 5. Visit and assessment schedule:

visits	baseline		
	1	2	3
	month 1/ enrollment	month 6	month 12
Vital signs	X	X	X
Height and weight	X		X
Physical examination	X		X
Concomitant medications	X	X	X
Adverse event reporting	X	X	X
Informed consent form	X		

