Events/issues which are part of the study objectives or endpoints will be systematically identified and collected from healthcare records or other applicable source records and summarized as part of any interim analysis and in the final study report. Such events do not need to be notified as individual reports to Takeda Pharmacovigilance.

Events/Issues which are not part of the study objectives and endpoints will not be abstracted or collected from healthcare records or other applicable source records.

Reporting of Adverse Drug Reactions to Regulatory Agencies and IRB/EC

LDRTC is responsible for reporting serious and non-serious adverse drug reactions suspected of being related to regulatory authorities. The Investigator is responsible for reporting adverse drug reactions to the IRB/EC, if required by national law or regulation, within the timelines required by such law or regulation. The Investigator shall maintain records of all such submissions.

Study-specific committees

No steering committee, data safety monitoring committee, or clinical endpoint committee will be used in this study.

STUDY OVERSIGHT

Premature Termination of Study:

[name], may prematurely terminate the study. Reasons for termination may include but is not limited to the following:

- Series of adverse events or incidences associated with subject participation.
- Low subject enrollment.

Clinical Research Quality Assurance:

To ensure that GCP and good clinical research are conducted per regulatory requirements and guidelines, the study will be made available for monitoring, auditing, review, and inspection by regulatory authorities such as IRB and FDA. This will be accomplished by providing direct access to study-related documents.

Data management

The acquired data will be entered into Excel for further analysis. Data will be analyzed using GraphPad Prism software (Graphpad Inc., La Jolla, CA) using ANOVA analysis and Student's t-test for statistical analysis. $p < 0.05$ is considered significant.

Samples and data storage

Once subjects have signed the informed consent form, they will be assigned a personal generic research study identification number. This number will be matched with the patient's name and demographic information in a file stored on a password-protected computer. Only members of the research team at **Lysosomal & Rare Disorders Research & Treatment Center, Inc** will have

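### The protocol aims at markers that detect kidney involvement, but the only analysis it fixes is a test of mean differences at p<0.05, which does not measure detection

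*Protocol*

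**What the plan says.** The aim is given under Study design and plan: "This prospective study aims to establish novel biomarkers for non-invasive detection of kidney involvement in FD". The primary objective, under Objective and Specific Aims, begins: "Identify biomarkers in urine for the detection and progression of kidney involvement in naïve male and female patients with FD".

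The analysis is given in two sentences under Data management. Data will be analysed "using ANOVA analysis and Student's t-test for statistical analysis", and p<0.05 "is considered significant". No contrast is tied to any objective there, and no measure of discrimination is named anywhere in the protocol.

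On numbers, the 50 subjects "include 25 healthy individuals and 25 patients with Fabry disease". Within the Fabry group, Study population lists "5 without clinical evidence of nephropathy and 15 patients with clinical evidence of nephropathy", plus 5 naïve patients who, by the note to cohort 3, may fall into cohort 1 or cohort 2. The three nephropathy subcohorts are all described as on ERT, whereas cohort 1 may be naïve or on ERT. Controls are people without Fabry disease and with no known kidney disease.

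Other parts are more modest. Study type reads "Descriptive and observational study of molecular components detected in biological specimens of urine", Aims 2 and 3 speak of association, and the introduction says that the biomarkers "may offer further insight on renal injury beyond current diagnostic tests".

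**The concern.** Detection is about individuals: given a marker value, can a patient with kidney involvement be told from one without? A t-test or ANOVA asks whether group means differ. A marker can pass the second question and do poorly on the first.

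The choice of contrast adds a second difficulty. Healthy controls differ from Fabry patients in both Fabry disease and kidney status, so a marker raised by Fabry disease alone could be significant at 25 vs 25 and say nothing about the kidney. The contrast closest to the objective is within Fabry patients, with versus without nephropathy. It is also the small one, at 15 vs 5.

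At stake is the central claim. If significance is the only result attached to the detection objective, the report can carry a list of significant markers without showing whether any of them would detect kidney involvement.

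**Working it through.** The protocol gives no effect size, standard deviation, power or performance target, so there is no figure of its own to reproduce. The check asks how well a marker discriminates when it only just meets the stated threshold.

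**Inputs from the protocol:** p<0.05 with Student's t-test (Data management); 15 vs 5 and 25 vs 25 (Study population).

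**Assumptions, not in the protocol:** two-sided testing; normal markers with equal variance; specificity of 90%, with 80% and 95% as the range.

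**Step 1. Smallest significant standardised difference.** d = t(0.975, n1+n2−2) × √(1/n1 + 1/n2).
- 15 vs 5: 2.101 × 0.516 = 1.085
- 25 vs 25: 2.011 × 0.283 = 0.569

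**Step 2. Discrimination at that difference.** AUC = Φ(d/√2); sensitivity = Φ(d − z), where z is 0.842, 1.282 or 1.645 for specificity 80%, 90% or 95%. The share missed is 1 − sensitivity.

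| Contrast | d | AUC | Missed at 80% spec. | Missed at 90% | Missed at 95% |
|---|---|---|---|---|---|
| Fabry with vs without nephropathy, 15 vs 5 | 1.085 | 0.78 | 40% | 58% | 71% |
| Fabry vs healthy, 25 vs 25 | 0.569 | 0.66 | 61% | 76% | 86% |

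For comparison, 80% sensitivity at 90% specificity needs d = 0.842 + 1.282 = 2.12, about twice the 15 vs 5 threshold.

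**Step 3. Precision of an AUC at these sizes.** Hanley-McNeil variance = [A(1−A) + (n1−1)(Q1−A²) + (n2−1)(Q2−A²)]/(n1·n2), with Q1 = A/(2−A) and Q2 = 2A²/(1+A), where n1 is the number with nephropathy. For an observed A = 0.80, Q1 = 0.667 and Q2 = 0.711.
- 15 vs 5: [0.160 + 14 × 0.0267 + 4 × 0.0711]/75 = 0.0109, so SE = 0.104 and the 95% CI is about 0.60 to 1.00 (upper limit cut at 1).
- All 5 naïve patients with nephropathy, 20 vs 5: about 0.61 to 0.99.
- All 5 naïve patients without nephropathy, 15 vs 10: about 0.63 to 0.97.

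**Step 4. What specificity can be observed.** With 5 patients without nephropathy, empirical specificity can only be 0, 20, 40, 60, 80 or 100%. The 90% in Step 2 therefore describes the model and could not be read off the data. Sensitivity is imprecise too: 12 of 15 detected (80%) has an exact 95% CI of 52% to 96%.

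**The case against.** The strongest reply has four parts.

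**The protocol never says that p<0.05 establishes a marker for detection.** A reader might infer this from the aim and the analysis sentence together, but Data management says only what counts as significant. The operative objective is to identify markers, the aims speak of association, and the study calls itself descriptive. This stands. The point is therefore a mismatch between aim and method; the protocol states no false decision rule.

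**The protocol never says that Fabry versus healthy will be read as kidney involvement.** It separates Fabry patients by nephropathy status and CKD stage and plans comparison with standard kidney measures. This also stands. What remains is that no contrast is linked to the detection objective, and that the largest one available cannot answer it.

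**ROC analysis is the kind of detail a SAP may supply.** Partly right: naming two tests does not exclude others, and a SAP that was not available might add them. But the protocol does fix a method, and that method answers a different question from its stated aim. The criticism is of what is written.

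**The figures are a boundary case.** They describe a marker that only just reaches significance under a simple model; stronger markers would do better. True, and the figures should be read as what the threshold allows, not as what will be found.

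A reader might also infer that a marker missing three quarters of patients with kidney involvement could pass. The documents do not support that as a general statement: 76% belongs to Fabry versus healthy at an assumed 90% specificity. In the contrast that bears on kidney involvement the figure is 58%.

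**Conclusion.** The concern holds in a limited form. The protocol pairs a detection aim with a mean-difference method, and passing that method's threshold is compatible with weak discrimination: in the within-Fabry contrast an AUC of about 0.78 with 40% to 71% of affected patients missed, and in Fabry versus healthy an AUC of about 0.66 with 61% to 86% missed. These ranges rest on two-sided testing, normal equal-variance markers and specificities of 80% to 95%, none of which the protocol states.

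The aim of establishing markers is also stronger than the sample can bear. However the naïve patients are classified in the three splits examined, an observed AUC of 0.80 has a lower confidence limit of only about 0.60 to 0.63. That supports calling a marker a candidate.

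The within-Fabry contrast has its own weakness, because nephropathy status is partly mixed with ERT status. It is the better contrast for the objective, but not a clean one. The study remains feasible and needs no more patients.

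**What to change.** Add one paragraph to the analysis text and change one phrase in the aim.

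- For the detection objective, report each marker's AUC with 95% CI for Fabry patients with versus without nephropathy. ANOVA and t-tests can stay as descriptions of group differences.
- Before the analysis, assign each naïve patient to cohort 1 or 2 by kidney status, and state the resulting group sizes. Show the results by ERT status as well.
- Do not report sensitivity at a fixed 90% specificity, since 5 patients without nephropathy allow only 20% steps. If sensitivity is shown, give it at an attainable specificity (such as 4 of 5), with exact CIs for both.
- Describe Fabry-versus-healthy differences as disease effects, not as evidence of detecting kidney involvement.
- In Study design and plan, replace the aim of establishing biomarkers with that of identifying candidate biomarkers.

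The cost is a little more analysis on data already planned, and a more modest claim.

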Eligibility (inclusion/exclusion)	X		
Urine pregnancy test (part of eligibility)	X		
HBV/HCV testing (if clinical results are not available)			
Medical history	X	X	X
Retrospective chart review	X		
Urine sample collection and urinalysis	X	X	X

STUDY METHOD AND PROCEDURES

Informed consent will be obtained prior to the execution of any research procedures. The subjects will be followed for a 12 month period during which urine will be collected three times every six months. Subsequent samples will be obtained based on the Principal Investigator's order. Biological samples are only collected for research purposes and will not be sold or distributed for other purposes.

After the study is completed, biological samples may be retained for possible future exploratory analysis by the Principal Investigator and/or by the Co-Investigator.

CONSENT/ASSENT:

Enrollment of a subject or a family member in this study will be completed once all inclusion and no exclusion criteria have been met and the subject has signed the informed consent form (ICF). The clinical research coordinator will approach subjects identified by the Principal Investigator.

The Principal Investigator will discuss the research study with the subject explaining research procedures, potential risks, and benefits. The Principal Investigator will give the subject an

opportunity to ask questions, and ample time will be given to the subject to review the ICF in detail. The clinical research coordinator will repeat this process using verbiage found in the consent to explain the study.

The alternative method for consenting:

The ICF could be emailed or mailed to the patient with a pre-paid addressed return envelope provided for convenience. The patient should be contacted at a later time to confirm receipt of the ICF and be given an opportunity to ask questions. The potential subject will have ample time to review the ICF in detail. Once all questions have been answered to the subject's satisfaction, research personnel should provide guidance as to what page requires the subject's printed name, signature, date, and witness signature (if applicable). A copy of the original signed ICF will be provided to the patient.

DEMOGRAPHICS AND MEDICAL HISTORY

A review of demographic parameters, including age, gender, race, and ethnicity, will be performed at screening.

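### Does Table 4 leave the CKD stage, and so membership of subcohorts 2a to 2c, undetermined?

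*Protocol*

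**What the plan says.** Under STUDY PROCEDURES, Study design and plan, three statements bear on staging:

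- The definition: "FD patients will be assessed using the definition of Kidney Disease Outcomes Quality Initiative (KDOQI) 2002".
- The GFR method: "The glomerular filtration rate will be calculated from serum creatinine (CKD-EPI").
- The pointer to the table: "The categorization of kidney involvement via renal biomarkers will be defined (Table 4").

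Table 4 (same bands in Table 3) gives stages 1, 2, 3a and 3b, with numeric rows for GFR, cystatin-C and urine B2M. It states no order of precedence among them.

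Under SUBJECT SELECTION, Study population, CKD stage separates the patients with nephropathy. Subcohort 2a is stage 1, 2b is "FD subjects on ERT with CKD stage 2 (estimation n=5") and 2c is "FD subjects on ERT with CKD type 3 a or b (estimation n=5"). Cohort 1, without nephropathy, is described by eGFR and albuminuria.

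BRIEF RATIONALE AND BACKGROUND gives two of the staging rows a second role: "Urinary biomarkers will then be compared to the standard measures of kidney function and proteinuria: GFR, cystatin-C, B2M, bikunin, NGAL". Table 2 lists the study laboratory's own assays as "B2M, bikunin, NGAL, osteopontin, clusterin, creatinin".

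**The concern.** The sentence that introduces Table 4 speaks of renal biomarkers in the plural, and the table offers three of them. Read literally, a patient could have three stages. GFR 62 with cystatin-C 1.3 is stage 2 (subcohort 2b) on the first row and stage 3a (subcohort 2c) on the second.

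The bands are also not a clean partition. GFR of exactly 90 has no stage, and some cystatin-C and B2M values have two. B2M is moreover a study assay and a listed comparator, so using it to set the stage would let a study measurement help define the groups it is compared across.

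At stake is who belongs to 2a, 2b and 2c. With 5 patients expected in each, one reassignment is 1/5 = 20% of a subcohort. A rule left open could in principle be settled after the urine results are known.

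**Working it through.** The protocol states no figure to reproduce here, apart from the subcohort total: 5 + 5 + 5 = 15, as given for patients with nephropathy.

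**Step 1: are the printed bands exhaustive and exclusive?** Inputs are the rows of Table 4.

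| Row | Stage 1 | Stage 2 | Stage 3a | Stage 3b |
|---|---|---|---|---|
| GFR | >90 | 60-89 | 45-59 | 30-44 |
| Cystatin-C | 0.5-0.9 | 1.0-1.2 | 1.3-1.5 | 1.4-1.9 |
| Urine B2M | none | 0.428-0.603 | 0.603-0.950 | 0.950-1.034 |

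Each value within the bands was checked for the number of stages it falls in.

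- GFR, whole numbers 30 to 120: only 90 has no stage, and no value has two.
- GFR to one decimal: 44.1-44.9, 59.1-59.9 and 89.1-90.0 have no stage. The first range lies inside 2c, which pools 3a and 3b. The other two lie between subcohorts. These gaps arise only if eGFR is not rounded. The protocol does not state rounding, but bands printed in whole numbers suggest whole-number values.
- Cystatin-C to one decimal: 1.4 and 1.5 are both 3a and 3b. Both stages are in 2c, so membership is unaffected.
- Urine B2M to three decimals: 0.603 is both stage 2 and 3a (2b or 2c), and 0.950 is both 3a and 3b (2c either way).

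**Step 2: which row does the protocol point to?**

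- The subcohorts are labelled by CKD stage, and the section that prints Table 4 names one staging definition and one way of calculating GFR.
- Cohort 1 is described by eGFR, not by cystatin-C or B2M.
- The same section judges decline by falling GFR and its slope.
- The table's wording of mild and moderate reduction sits directly above the GFR row.
- No sentence stages a patient by cystatin-C or B2M alone.
- The B2M row cannot serve as a staging rule, since it has no stage 1 band and so cannot place anyone in 2a. B2M is also assayed by the study laboratory, and urine is frozen until screening, whereas the cohorts are set out under subject selection.

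**Step 3: what stays open once GFR leads?** The cystatin-C and B2M overlaps drop out, and so does the conflict between rows. With whole-number eGFR the only unplaced value is 90, on the 2a/2b boundary. The control column appears to give 90 as the minimum for normal function, so placing 90 in stage 1 is the obvious choice.

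**Step 4: does it reach an analysis?** Data management names ANOVA, Student's t-test and p < 0.05, and assigns none of them to 2a-2c.

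**The case for a change.** The best case for a change is that GFR precedence can be inferred but not cited. The KDOQI sentence says how patients are assessed. It does not say that the other two rows are only descriptive, and a later sentence hands the categorisation to the table as a whole. The flawed bands are printed in the protocol itself, so this is more than detail left to an analysis plan. Specific aims 2 to 4 relate urinary markers to kidney involvement, so stage could well become a grouping factor. Correcting the text would be cheap.

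The textual facts stand: there is no precedence sentence, 90 is unplaced and some bands overlap. The consequences drawn from them are weaker.

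- Conflict between rows matters only if cystatin-C or B2M stages patients, and the surrounding text points away from that. The protocol gives no rate of disagreement, so any probability of a misplaced patient would rest on an assumed rate.
- The comparator argument does not single out B2M. The same sentence lists GFR and cystatin-C as comparators, so staging by GFR would also let a listed comparator define the groups.
- Nothing in the protocol suggests that the staging row would be chosen after the assays are read.
- Table 5 lists no serum creatinine, but it does list "Retrospective chart review" at visit 1, and Table 2 places GFR among the clinical laboratory measures. A source outside the study visits is therefore foreseen.

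**Conclusion.** No change to the plan is needed. The missing precedence sentence is a gap that an analyst following the protocol would fill in one way, by staging on CKD-EPI eGFR. The skipped value is a clerical slip at one boundary. What remains is one whole-number eGFR value, 90, between 2a and 2b. A patient with that value would be 20% of a 5-patient subcohort, but would move only between adjacent groups to which the protocol ties no test.

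This rests on two assumptions: that GFR is the staging measure, which the text supports without saying so outright, and that eGFR is reported in whole numbers. If eGFR were kept to one decimal, 59.1-59.9 and 89.1-90.0 would also fall between subcohorts, and ordinary rounding would settle all of these except those that round to 90. Tidier tables would read better, but no result or conclusion is shown to depend on them.
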